10.1 Primary study estimand and parameter(s)

10.1.1 Definition of the primary estimand

Participants aged ≥18 years with at least 2 symptoms suggestive of COVID-19 or COVID-likeillness (one respiratory and one systemic) and meeting the IP eligibility criteria, what is the between group difference, estimated by a hazards ratio, in time to first self-report of feeling recovered (TTR) after treatment with an IP compared with placebo or comparator, regardless of treatment discontinuation for any reason or feeling better before starting the medication, and in conjunction with concomitant medication (including anti-viral medication) as necessary? Participants who die within 28 days from randomisation will be censored at 28 days. TTR is measured by response to the daily diary question "do you feel recovered today from your respiratory infection?", and censored at 28 days after randomisation.

Attributes of estimand:

Population – people in the community aged ≥18 years with at least 2 symptoms suggestive of COVID-19 or COVID-like-illness (one respiratory and one systemic) and meeting the IP eligibility criteria.

Treatment conditions – IP compared with placebo or comparator, regardless of treatment discontinuation for any reason or feeling better before starting the medication, and in conjunction with concomitant medication (including anti-viral medication) as necessary. Participants who die will be given a worst-case value and censored at 28 days.

Outcome variable – time to first self-report of feeling recovered, as measured by response to the daily diary question "do you feel recovered today from your respiratory infection?", censored at 28 days after randomisation.

Handling of intercurrent events – treatment policy strategy applied to study treatment discontinuation, feeling better before starting the medication and use of concomitant medication (including anti-viral medication). Composite strategy applied to death within 28 days of randomisation.

Population level summary measure – hazard ratio.

10.1.2 Estimator

Analysis will include all eligible randomised participants with at least one follow-up time point (any diary data or information from the 28-day follow-up call) in the group to which they were randomised, regardless of subsequent treatment received. A Bayesian piecewise exponential model with weakly informative priors will be used to estimate the hazard ratio for the time to first self-report of feeling recovered within 28 days of randomisation, adjusting for stratification variables and using all observed data (including data observed after treatment discontinuation and irrespective of use of concomitant medication or feeling better before starting the medication, except for participants who die within 28 days of randomisation who will be censored at day 28.

The primary endpoint is time to recovery, as defined by the first instance that a participant reports this. The primary analysis will be a Bayesian piecewise exponential model with weakly informative priors (specified in the M-SAP), with endpoints regressed on treatment and

stratification covariates. Let θ_j denote the log hazards ratio comparing the hazards of recovery for participants in treatment group *j* versus participants in the comparator arm. We will test the hypothesis that:

 $H_0: \theta_j \leq 0$

 $H_1: \theta_i > 0$

If the Bayesian posterior probability of superiority (a log hazards ratio greater than 0 corresponding to quicker return/recovery) for a treatment versus control is sufficiently large (e.g. >= 0.99), the null hypothesis will be rejected and the intervention will be deemed superior to control. The exact threshold of the superiority decision criterion will be determined a priori via simulation to control the one-sided type 1 error of the study at approximately 0.025, and will be specified in the M-SAP.

We will carry out sensitivity analyses to explore the robustness of inferences from the main estimator to deviations from its underlying modelling assumptions and limitations in the data. This may include fitting an adjusted Cox proportional hazards model. A supplementary analysis using an unadjusted log-rank test may also be performed. All sensitivity and supplementary analyses will be specified in the M-SAP.

The pattern of missingness will be reported, for instance if there is a difference by group in the proportion of participants lost to follow-up, with no post-baseline data, and withdrawals. We will also check for a pattern of missingness related to intercurrent events. If the pattern of missingness differs between groups, relevant imputation methods will be used to take account of this and an additional sensitivity analysis carried out using imputation.

If an IP is evaluated in a phase IIa-type evaluation, the first interim analysis will use viral clearance and possibly impact on biomarkers as the primary outcome, and will only progress to the next stage of the trial if the IP is looking promising enough. Precise definitions and rules will be specified in the M-SAP.

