All participants will receive an end-of-treatment telephone call assessment at day 14 (window 14-18 days) after randomisation. During this call diary completion, questions related to feeling recovered and return to usual activity, IP intake, health care utilization, and (serious) adverse events ((S)AEs) not reported in the diary will be captured.

In addition, participants will receive a telephone call at day 28 (window 28-35 days) after randomisation in case their diary is incomplete to capture a minimal outcome set. Longer-term follow-up will be at 3 and 6 months by electronic questionnaire (online, app) with back-up telephone call if not completed by other means. Specifically, these calls/questionnaires will capture data on whether the participant feels recovered from their index illness, participant's reported overall wellbeing, long-term consequences of the illness, healthcare utilization related to persisting symptoms, and impact of ongoing symptoms on activities.

For more details on study procedures, see section 8.3 Study Procedures. More study specific requirements will be described in the ISA.

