8.3.2 Follow-up

For 28 days

- Daily diary:
 - Questions related to feeling recovered
 - o Questions related to return to usual activity
 - o Individual symptoms with severities
 - o (Serious) adverse events
 - Participant reported overall wellbeing
 - o IP intake
 - Other medication intake
 - o Impact of symptoms on daily activities
 - New cases in households of participants
- Weekly diary:
 - Health care utilization
 - Complications
- Swab will be (self-)taken on day 4, 7 and 14

Telephone call day 14 (+4) as end of treatment visit:

- Completion of diary
- Questions related to feeling recovered and return to usual daily activity
- IP intake
- Health care utilization
- (Serious) adverse events

Telephone call day 28 (+7) in case diary data capture is not complete to capture a minimal outcome dataset

- o Questions related to feeling recovered and return to usual daily activity
- o IP intake
- Health care utilization
- o (Serious) adverse events

Follow up 3 months

- Questions related to feeling recovered
- o Questions related to return to usual activity
- Questions related to longer-term consequences of COVID-19 or COVID-like-illness
- o Impact on daily activities
- o Participant reported overall wellbeing
- Healthcare utilization

Follow up 6 months

- Questions related to feeling recovered
- Questions related to return to usual activity
- Questions related to longer-term consequences of COVID-19 or COVID-like-illness
- Impact on daily activities
- Participant reported overall wellbeing
- Healthcare utilization

Unscheduled call:

In case a participant discontinues the study due to the occurrence of a (S)AE, potentially related to the IP, the Site Investigator or delegate contacts the participant by telephone. In case of an SAE, a SAE form will be completed.

Contact details will be collected from the participants at baseline, including mobile and/or home telephone numbers to enable the collection of follow-up data.

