10.6 Definition of population for analysis

For each intervention, the primary analysis population is defined as participants who were randomised to that intervention or the usual care arm and eligible for randomisation to that intervention, during the same time frame when the intervention was actively randomising (i.e. Concurrent Randomised and Eligible Analysis Population) and have at least one post-baseline measurement.

Primary Analysis Set:

For each IP, all participants randomised to either the IP or its comparator (placebo or usual care and eligible for the IP). Participants later found to be ineligible (randomised in error) will be excluded. Non-concurrent comparators will not be included.

Safety Analysis Set:

All participants who took at least one dose of IP.

Symptomatic Analysis Set:

Primary Analysis Set restricted to those participants who report having the symptom at baseline.

Symptom Free Analysis Set:

Primary Analysis Set restricted to those participants who report not having the symptom at baseline.

Virology Analysis Set:

To be defined

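### The entry rule for the primary analysis omits the day-14 call and death, and Sections 10.1.1, 10.1.2 and 10.6 disagree on who is analysed and whether recovery reported by telephone counts

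*Protocol*

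**What the plan says.** Protocol Section 10.1.2 (Estimator) includes eligible randomised participants "with at least one follow-up time point (any diary data or information from the 28-day follow-up call"). For those included, the model works "using all observed data (including data observed after treatment discontinuation and irrespective of use of concomitant medication", and the endpoint is time to recovery, "as defined by the first instance that a participant reports this". The same paragraph censors deaths within 28 days at day 28.

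Section 10.1.1 defines the outcome variable as "time to first self-report of feeling recovered, as measured by response to the daily diary question". On deaths it states: "Composite strategy applied to death within 28 days of randomisation".

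Section 3.2 states: "All participants will receive an end-of-treatment telephone call assessment at day 14 (window 14-18 days) after randomisation". Section 8.3.2 lists the same item under both the day-14 and the day-28 call: "Questions related to feeling recovered and return to usual daily activity". The day-28 call is made only when the diary is incomplete.

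Section 10.6 describes the analysis population twice. The opening paragraph requires participants to "have at least one post-baseline measurement" and does not list the sources. The Primary Analysis Set below it takes all participants randomised to the product or its comparator, less those found ineligible, with no follow-up requirement.

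**The concern.** The entry rule admits the conditional call (day 28) and leaves out the universal one (day 14). A participant with a known recovery status at day 14 can therefore be left out of the primary analysis. So can a participant who dies early, although the estimand counts that person as not recovered to day 28. Removing an early death takes a non-recovered person out of the risk set, which flatters the arm in which the death occurred.

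The sections also leave open whether a recovery known only from a call is an event. The protocol states these rules itself, so the difficulty is conflict between them and not detail left to the M-SAP. Two analysts could build different primary data sets from the same protocol. The endpoint also drives interim decisions on success and futility (10.4), so that choice should not be open once data are seen.

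**Working it through.** **Who is in.** Each type of participant is set against the three rules:

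| Participant | 10.1.2 entry rule | 10.6, opening paragraph | 10.6, Primary Analysis Set |
|---|---|---|---|
| Some diary data | in | in | in |
| No diary, day-28 call answered | in | in | in |
| No diary, day-14 call only | **out** | in | in |
| Death before any diary entry, no call information | **out**, though the same paragraph censors deaths at day 28 | unclear: is a death record a measurement? | in |
| No contact after baseline | out | out | in |

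The rules agree in the first two rows and disagree in the last three.

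**What counts as an event.** Take an included participant with no positive diary answer who tells the day-14 caller that they have recovered. Under 10.1.1 this is not an event, because only the diary question measures the outcome. Under 10.1.2 it is, because all observed data are used and the first report defines recovery. The 10.1.1 wording would also rule out recovery reported at the day-28 call, which 10.1.2 accepts as follow-up. The two sections cannot both be followed literally.

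**How many the entry rule could remove.** The protocol gives no sample size (4.4 defers it to the ISA), diary return rate or contact rate. The figures here are assumptions: 300 per arm, 5% with no diary, 85% reached at day 14, contact at days 14 and 28 independent.

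Lost per arm = 300 × 0.05 × 0.85 × (1 − day-28 reach)

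- Day-28 reach 0%: 300 × 0.05 × 0.85 × 1 = 12.75, about 13.
- Day-28 reach 85%: 12.75 × 0.15 = 1.9, about 2.

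Deaths before a diary entry cannot be counted from the protocol.

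**What a strict diary-only reading could do.** This simulation adds two assumptions to those above: a control median of 10 days, and a further share of participants who stop the diary on recovery without reporting it. The model was piecewise exponential (0–7, 7–14, 14–28 days), fitted by maximum likelihood with interval censoring. Rejection was z > 1.96 using the empirical SD, a nominal one-sided 2.5%. There were 3,000 trials per row at 0% day-28 reach and 600 at 85%. Day-28 answers are used where obtained.

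| True HR | Stoppers, Usual Care vs product | Day-28 reach | Day-14 answer ignored | Day-14 answer used |
|---|---|---|---|---|
| 1.0 | 12% vs 4% | 0% | HR 1.09, rejection 15% | HR 1.05, 7% |
| 1.0 | 12% vs 4% | 85% | HR 1.045, 7.3% | HR 1.03, 4.2% |
| 1.0 | 8% vs 4% | 0% | HR 1.04, 6.3% | HR 1.02, 4.2% |
| 1.0 | 8% vs 4% | 85% | rejection 4.5% | 4.2% |
| 1.25 | 10% vs 10% | 0% | no bias, power 66% | power 69% |

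Monte Carlo error in the 600-trial rows is about 0.8 points near 4.5%, so the fourth row shows no difference.

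The bias comes from the stoppers. They have diary entries and therefore pass the entry rule. The 5% without a diary are equal between arms and unrelated to recovery in this set-up, so leaving them out costs information but adds no bias. The table thus measures the diary-only reading of the outcome, not the entry rule.

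**The case against.** The parenthesis in 10.1.2 says who is included, not which data are used. For anyone with one diary entry or a day-28 call, nothing in that section sets aside a day-14 answer. This stands. A reader might infer that the plan throws away the day-14 recovery status of every participant, but the text supports that only where the day-14 call is the sole follow-up. For everyone else the documents conflict; they do not prescribe a loss.

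The day-14 call is also a route for diary data. Section 3.2 allows diaries to be completed by telephone, and 8.3.2 lists diary completion first among the call items. This stands too, and it may make the call-only group very small.

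A reader might also infer a type 1 error near 15%. That figure needs a threefold imbalance in diary stopping that no document suggests, and none of those affected reached at day 28. The day-28 call exists for exactly these people and has a seven-day window. The argument that only product arms keep an intake record covers seven days of use, not the 28-day diary. With 85% day-28 reach, the same imbalance gives 7.3% before any change to the rule.

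Section 10.1.2 also promises a report of missingness by group and, if the pattern differs, imputation in an additional sensitivity analysis. That helps, but it does not settle who belongs in the primary analysis, and imputing an answer already collected is second best. On deaths, the specific censoring rule could be read as overriding the general entry rule. That is probably the intent, but the text does not say so.

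Finally, a reader might infer that at an interim analysis the day-14 call would be the only recovery data held for recent paper-diary participants. Section 9.2.3 says only that some SAEs may be found in diaries received after day 28, and interim timing is left to the M-SAP.

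**Conclusion.** The point holds as a conflict between sections. Section 10.1.2 read literally excludes two groups that 10.1.1 or 10.6 would keep: participants known only from the day-14 call, and participants who die before any diary entry. Sections 10.1.1 and 10.1.2 also disagree on whether a call can supply the event. None of this depends on the simulation.

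The number affected is probably small. The 2 to 13 per arm shown above rests wholly on assumed rates. Any bias depends on diary loss differing between arms, most plausibly in the open comparison with Usual Care, and on how many participants are reached at day 28. With equal loss the illustration shows no bias and about 3 points of power (66% against 69%). The 15% is an upper illustration and should not be cited as the expected error rate. The change is still worth making because it is cheap and removes a choice that could otherwise be made after data are seen.

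**What to change.** - Use one population rule in 10.1.2 and 10.6. Follow-up is any diary entry, the day-14 call, the day-28 call, or a recorded death by day 28. Make both descriptions in 10.6 match it.
- Enter every death by day 28 as not recovered to day 28, whether or not a diary exists.
- Align 10.1.1 so that recovery reported at a call counts when there is no positive diary answer. Treat it as interval-censored between the last negative diary entry (or day 0) and the call. A negative answer at the call extends follow-up to the call date.
- Add a diary-only sensitivity analysis.

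The cost is a few sentences in 10.1.1, 10.1.2 and 10.6, and an interval-censored term in the piecewise exponential likelihood, whose detail can sit in the M-SAP. No new data are collected. The drawback is that some primary outcomes are then elicited by staff over the telephone, which matters most in the open comparison; the diary-only analysis shows how far the result depends on them.

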8.1.4 Other study parameters to be recorded in the CRF

Demographics

- Age (years)
- Sex at birth (male/female/not specified)
- Ethnicity
- Household (living with others (yes/no), how many people, age of household, living situation)
- Regular paid work (yes/no)

- Healthcare worker (yes/no)

Relevant comorbidities and medication at baseline

- Relevant comorbidities ((e.g. cardiovascular disease, lung disease, asthma, diabetes, joint disease, neurological disease, severe mental illness, weakened immune system, other comorbidities) that started before inclusion in the study

Vaccination history

- COVID-19, influenza, pneumococcal and RSV vaccination status

Prior COVID-19

- Prior confirmed COVID-19
- Previous A&E/hospital overnight admission for COVID-19

Signs and symptoms at presentation

- Individual respiratory symptoms at presentation
- Overall illness severity (clinician's impression)
- Number of days with respiratory symptoms (days)

Anthropometrics

- Body weight (kg): self-reported or measured by recruiter
- Height (cm): self-reported or measured by recruiter
- Body mass index (BMI) will be calculated using the following formula: BMI = Body weight (kg)/(Height [m])²

Lifestyle parameters

- Smoking (never, former, current, unknown)

Clinical assessments

- Body temperature (°C) measured using available device (self-reported if central/remote inclusion, self-measured using TempaDOTs, or measured by recruiter)
- Peripheral oxygen saturation level as measured non-invasively by pulse oximetry, systolic/diastolic blood pressure, respiratory rate, heart rate (if inclusion is face-to-face)

Usual care provided

- Prescribed medication
- Advice given

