8.2 Randomisation, blinding and treatment allocation

8.2.1 Randomisation

With each new IP entering the platform, the randomisation ratio will be adapted. The day of randomisation will be Day 0. Treatment initiation will be as close to Day 0 as possible, using methods that may include directly dispensing IP to participants, or couriering medications to participants who are recruited centrally.

Included patients will be allocated to either an IP arm or a control arm. Each IP has a matching placebo or comparator. For specific IPs Usual Care can be a control arm (specified in ISA). When there is more than one arm with matched placebos in the trial simultaneously, placebos will be pooled for the primary analysis. This means that allocation will be split equally between all active IP arms the participant is eligible for, and placebo. For example, if there are 2 IPs with matching placebo randomisation will be 1:1:1 (Active A):(Active B):(Placebo), and within Placebo allocation will be 1:1 (Placebo A):(Placebo B). Primary analysis for a particular IP will include all participants allocated to placebo who were eligible for the IP and randomised in the same time frame, i.e. concurrent and eligible placebo participants. Potential participants can be included if they are eligible to be randomised to at least one IP. The trial will start with three trial arm 1:1:1.

Participants will be randomised using a rapid, secure, web-based randomisation system using non-deterministic minimisation, with a random element. The minimisation factors will be age (<55/≥55 years), time since onset of symptoms (≤2/>2 days), and country (Belgium/France/Germany/Ireland/Poland/Spain/UK). The randomisation sequence will be saved electronically in a working environment with restricted access.

Participants randomised to a treatment arm will be allocated to an IP pack according to the randomisation number. This individual investigational product pack will be dispensed to participants once they are randomised.

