The impact on biomarkers, for example illness severity or immunological response, is dependent on the specific IP. If this will be an outcome parameter, it will be specified in the ISA.

Viral mutations

Raw sequencing reads will undergo quality assessment using FastQC, followed by quality trimming with TrimGalore v. 0.6.7 (https://github.com/FelixKrueger/TrimGalore), and reference mapping against the SARS-CoV-2 genome (GenBank: NC_045512.2) using the CLC Genomics Workbench v.9.5.3 (Qiagen). Clade and lineage assignment will be performed for all SARS-CoV-2 consensus sequences using Nextclade v.2.2.0 (https://clades.nextstrain.org) and Pangolin v1.9 (4.0.6) (https://pangolin.cog-uk.io), respectively. SARS-CoV-2 genome sequencing will be considered successful if: i) the resulting genome sequence harbored < 15% ambiguous base calls (Ns) in the consensus sequence, and ii) was successfully classified by both Pangolin and NextClade. For detection of genetic variants, trimmed reads will be mapped against the SARS-CoV-2 genome (GenBank: NC_045512.2) using the CLC Genomics Workbench v.9.5.3 (Qiagen) with a length and a similarity fraction of 0.7 and 0.99, respectively.

Other sampling

Specific biological marker levels and immunological response are dependent on the IP, and will be specified in the ISA.

Table 1. Schedule of Assessments

| | Baseline and Start study | | Follow-up | | | |
|--|----------------------------------|--|--------------------------------|--------------------------------|----------|----------|
| | Day 0 Screening/Randomisation | Days 1-28 | Telephone call 14 (+4) days | Telephone call 28(+7) days⁴ | 3 months | 6 months |
| Informed consent | х | | | | | |
| Demographics | х | | | | | |
| Relevant comorbidities and medication | х | | | | | |
| Randomisation | х | | | | | |
| Anthropometrics, lifestyle parameters | х | | | | | |
| Clinical assessments | x ² | | | | | |
| Vaccination and COVID-19 history | х | | | | | |
| Usual Care provided | х | | | | | |
| Virology sampling (swab) | x ¹ | x ¹ | | | | |
| Dispensing study product | х | | | | | |
| Return to usual activity and recovered | | Daily | х | х | х | x |
| Symptoms with severities | х | Daily | | | | |
| Participant reported overall wellbeing | х | х | | | х | х |
| Impact on daily activities | | Daily | х | х | х | x |
| Household transmission | | Daily | | | | |
| IP intake | x ³ | Daily ³ | х | х | | |
| Health care utilization | | Weekly | х | х | | |

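### The primary model adjusts only for the minimisation factors and leaves out baseline illness severity, which the trial already records; if severity is prognostic, power is lost

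*Protocol*

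**What the plan says.** Protocol 10.1.2 gives the covariates of the Bayesian piecewise exponential model twice. The first statement is "adjusting for stratification variables and using all observed data". The second has the model "with endpoints regressed on treatment and" the stratification covariates. No other covariate is named.

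The protocol lists no factors under the word stratification. The nearest match is 8.2.1, which describes minimisation: "The minimisation factors will be age (<55/≥55 years), time since onset of symptoms (≤2/>2 days), and country" (seven levels). Reading the stratification variables as these three factors is an inference, but the only one the text allows.

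Severity at entry is recorded. Section 8.1.4 lists "Overall illness severity (clinician's impression") among the signs and symptoms at presentation. Table 1 in 8.3.3 marks "Symptoms with severities" and "Participant reported overall wellbeing" at day 0. Section 8.1.4 also has "Individual respiratory symptoms at presentation", but there without grades.

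Section 10.1.1 takes the hazard ratio as the summary measure, for an endpoint that is the participant's own report of feeling recovered, censored at 28 days. Section 4.4 leaves sample size to the intervention-specific appendices. Section 10 leaves full analysis detail to the M-SAP.

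**The concern.** Entry is syndromic: an adult with one respiratory and one systemic symptom qualifies, whatever the pathogen, provided hospital admission is not needed that day. Severity at entry can therefore vary widely, and participants who start sicker can be expected to report recovery later. A baseline measure of severity is an obvious candidate covariate, and the trial collects one at no extra cost.

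The hazard ratio is non-collapsible. When a prognostic covariate is left out of a hazard model, the estimated treatment hazard ratio sits closer to 1 than the ratio conditional on that covariate, and the test loses power. The same model feeds the interim decisions in 10.4. Because later products are to follow the same core structure (3.1), any loss would recur with each product added.

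**Working it through.** **No figure to reproduce.** The protocol states no sample size, event number, power or target hazard ratio. What follows gives scale only.

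**Inputs from the protocol.** One-sided type 1 error of about 0.025 (10.1.2); 1:1 within each pairwise comparison, from the 1:1:1 start (8.2.1); censoring at day 28 (10.1.1).

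**Assumed inputs.** Hazard ratio 1.2 or 1.3; median recovery 8 days; daily reporting; severity a standard normal score, independent of age and onset, with a log-hazard effect of 0 to 0.7 per SD; one look at z > 1.96. A Cox model stands in for the Bayesian model. Both models adjust for age group and onset group; country was not simulated.

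**Step 1: events for 80% power** (Schoenfeld, 1:1): 4(1.96 + 0.8416)² / (ln HR)².
- HR 1.2: 31.40 / 0.03324 = 945 events. With 90% of participants assumed to have an event, n = 945 / 0.9 = 1050.
- HR 1.3: 31.40 / 0.06884 = 457 events. n = 457 / 0.9 = 508 (rounded up to an even number).

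**Step 2: simulate with and without severity**, 1000 trials per setting. The effective sample size ratio is (mean z with severity / mean z without)², since mean z grows with the square root of n. At 1000 trials the Monte Carlo standard error of a power near 0.75 is √(0.75 × 0.25 / 1000) = 0.014.

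| True HR | Log-hazard SD (HR per SD) | Estimated HR without → with | Power without → with | Effective n ratio |
|---|---|---|---|---|
| 1.2 | 0 (1.00) | 1.192 → 1.192 | 0.795 → 0.791 | 1.000 |
| 1.2 | 0.2 (0.82) | 1.185 → 1.191 | 0.751 → 0.774 | 1.053 |
| 1.2 | 0.35 (0.70) | 1.177 → 1.194 | 0.714 → 0.781 | 1.173 |
| 1.2 | 0.5 (0.61) | 1.165 → 1.190 | 0.648 → 0.769 | 1.301 |
| 1.2 | 0.7 (0.50) | 1.144 → 1.185 | 0.522 → 0.753 | 1.583 |
| 1.3 | 0 (1.00) | 1.285 → 1.286 | 0.782 → 0.775 | 0.999 |
| 1.3 | 0.2 (0.82) | 1.269 → 1.278 | 0.753 → 0.776 | 1.060 |
| 1.3 | 0.35 (0.70) | 1.262 → 1.288 | 0.711 → 0.772 | 1.172 |
| 1.3 | 0.5 (0.61) | 1.238 → 1.277 | 0.626 → 0.745 | 1.309 |
| 1.3 | 0.7 (0.50) | 1.216 → 1.281 | 0.540 → 0.755 | 1.586 |

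**Step 3: a second set of assumptions.** With 300 per arm, HR 1.3, a posterior threshold of 0.99 (z > 2.326) and an unadjusted comparison model, the gains were about 0% at SD 0, 1-2% at 0.1, 6% at 0.2, 10-12% at 0.3, 29-32% at 0.5 and 51-57% at 0.7. The two sets agree.

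**Step 4: what the SDs mean.** The hazard ratio between participants 1 SD below and 1 SD above mean severity is exp(2 × SD): exp(0.4) = 1.5, exp(0.6) = 1.8, exp(1.0) = 2.7 and exp(1.4) = 4.1 for SDs of 0.2, 0.3, 0.5 and 0.7.

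**Step 5: overlap.** If the existing covariates explain a share R² of severity, roughly SD × √(1 − R²) remains to be gained from. An SD of 0.5 falls to 0.35 when R² = 1 − (0.35/0.5)² = 0.51, and the gain falls from about 30% to about 17%.

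**Step 6: type 1 error.** Under the null (3000 trials, n = 600, severity SD 0.5) the rejection rate was 0.019 without severity and 0.018 with it. Both are slightly conservative because of tied days.

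**The case against.** Adjusting for the balancing factors is a conventional and valid choice. Section 10 calls itself an overview and leaves detail to the M-SAP, and 10.1.2 allows an adjusted Cox sensitivity analysis whose covariates are not yet listed. All of that stands, so this is a matter of efficiency and not an error. It does not remove the point. Section 10.1.2 sends the priors, the threshold and the sensitivity analyses to the M-SAP but states the covariate set itself, twice. A sensitivity analysis does not drive the interim decisions.

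It is also fair that the size rests on assumptions. Nothing in the protocol says how strongly severity predicts recovery in ambulatory patients, and at an SD of 0.1 the gain is only 1-2%.

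Four stronger readings are tempting and are not supported:
- **That the hazard ratio is biased.** The model without severity targets a different hazard ratio, one not conditional on severity. Type 1 error is unaffected, and chance imbalance in severity is already part of the posterior uncertainty.
- **That age and time since onset enter the model only as two-level factors.** Section 8.2.1 dichotomises them for minimisation; 10.1.2 says nothing about their coding.
- **That the onset factor carries little information because the initial arms require onset within 3 days.** No distribution of onset days is given, and the master protocol also admits products with onset under 7 days.
- **That graded symptoms and wellbeing are in 8.1.4 as covariates fixed before allocation.** Only Table 1 shows them, in a day-0 column that also contains randomisation.

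**Conclusion.** The point holds as a loss of efficiency, not of validity. The stated primary model leaves out baseline illness severity, which the trial already records and which can be expected to predict the endpoint. If it does, the estimated hazard ratio moves towards 1 and power falls. In effective sample size, adding severity is worth about 0% if severity has no effect, about 5-12% at a log-hazard SD of 0.2-0.3, about 30% at 0.5 and about 50-60% at 0.7, and less with overlap. This range rests on the assumed hazard ratio, median, sample size and severity SD, a single look, and a Cox model in place of the Bayesian one; the protocol supplies none of the design figures needed to narrow it. Adjusting costs almost nothing if severity turns out not to matter.

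**What to change.** - **Section 10.1.2:** name the covariates instead of calling them stratification variables, and add one prespecified baseline severity covariate to age, time since onset and country. The clinician's overall severity rating is the simpler choice. A day-0 symptom score would also serve if its recording before randomisation is ensured. State the coding and a simple rule for missing values.
- **Timing:** require the chosen measure to be recorded before allocation. Section 8.3.1 lists the baseline form ahead of allocation but does not make the order a rule. It matters most for the Usual Care comparison, which 8.2.3 says is not double-blind.
- **Section 10.1.1:** state that the hazard ratio is conditional on the listed covariates. This is needed already for the three existing factors, and adding severity changes the target.
- **Interim analyses and Simulation Report:** use the same model, so that the decision thresholds are calibrated for the analysis actually run.

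The cost is wording in the protocol and M-SAP and a rerun of the simulations. No new data item is needed.
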